11.1.2.1 Dose Escalation

All evaluable subjects will be analyzed for dose escalation, which are those completing Week 4 or those withdrawing early for experiencing a DLT. Number and percentage of subjects with and without DLT will be presented according to DL.

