8.4.7 Dose-limiting Toxicity

The DLTs and MTD are defined using the NCI CTCAE version 4.03.

Dose-limiting toxicities will be drug-related toxicities (considered related or possibly related to) and graded using NCI CTCAE version 4.03 occurring during the DLT period and include:

- Non-hematologic toxicity \geq grade 3 (except diarrhea, nausea, and vomiting unless lasting >3 days despite optimal supportive care)
- Confirmed (with a second measurement after 24 hours) non-hematologic appropriately graded laboratory findings of grade ≥ 3 that were \leq grade 1 at baseline
- Hematologic toxicity:

- Grade 4 neutropenia ≥ 5 days, or grade 3 neutropenia with fever (fever is $> 38.4^{\circ}\text{C}$)
- Grade 4 thrombocytopenia, or grade 3 thrombocytopenia lasting > 7 days or with bleeding
- Any other toxicity assessed as related to RGT100-PEI, and which, in the opinion of the study Investigator(s) and the Sponsor physician constitutes a DLT

The DLT period will be 4 weeks. Evaluation of the available safety data over this DLT period will be required from at least 3 subjects per DL and per Group (A or B) before a decision is made whether to enroll additional subjects at the same, or the next DL.

Note: Subjects withdrawn from the study before the completion of the DLT period for reasons other than DLT will be replaced.

During dose escalation, escalation to the next DL will occur only if the safety and tolerability (including DLTs) data are acceptable as determined during the dose escalation meetings by the SRC. If any change is made to the grade or causality of an AE during the study that may alter its DLT status, the Sponsor and SRC must be informed immediately as this may affect dose escalation decisions.

The following toxicities will not be considered as DLTs:

- Grade 3 AE of tumor flare (defined as local pain, irritation, or rash localized at sites of known or suspected tumor)
- Grade 3 irAE that resolves to grade ≤ 1 within 7 days.

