8.4.9 Selection and Timing of Dose for Each Subject

8.4.9.1 Dose Escalation Phase

The planned DLs to be investigated are presented in Table 2 below.

Table 2: Dose Levels for RGT100-PEI Dose Escalation

Dose Level	RGT100-PEI Dose	Volume of RGT100-PEI to be Injected
1	0.2 mg	1 mL
2	0.4 mg	2 mL
3	0.6 mg	3 mL
4	0.8 mg	4 mL

RGT100-PEI will be administered by intratumoral/intralesional injection. A dose escalation meeting with the SRC (refer to [Section 10.5](#) for SRC details) will be held to evaluate a dose escalation after all subjects in a DL per group have completed the DLT period.

Group A: Dosing for Group A (cutaneous lesions) will start first. The total dose will be administered each on 2 separate days of every week (Mondays and Thursdays or Tuesdays and Fridays) for a maximum of 4 weeks.

Group B: Dosing for Group B (liver lesions) will start once DL2 has proven to be safe in Group A. Dosing in Group B will then start at DL2. The total dose will be administered on 1 day of every week for a maximum of 4 weeks.

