8.4.9.4 Dose Modification and Dose Delay

Every effort should be made to administer trial treatment on the planned schedule. If a dose is missed, the dose should be administered as soon as possible. There should be at least 2 days between consecutive injections.

Treatments visits can be moved by 1 day when necessary for logistical purposes.

The End-of-Treatment Visit (Day 29) can be moved by ± 3 days and follow-up visits can be moved by ± 7 days when necessary.

The toxicity of treatment must be recorded before the administration of the next dose and graded according to the current version of the NCI CTCAE version 4.03. If individual

subjects experience treatment-related toxicity, subsequent trial treatment may be delayed as described below. Dose reductions are not permitted.

For grade 3, grade 4, or intolerable grade 2 toxicities, the treatment will be interrupted until recovery to \leq grade 1 or to baseline. Trial treatment will be permanently discontinued if the subject fails to recover to this extent within 3 weeks. Dose reductions or modifications are not allowed in both, the dose escalation and expansion phase.

If a subject cannot tolerate treatment despite the dose delays, trial treatment will be discontinued. The subjects will then undergo end of treatment visit and will be followed up according to plan.

In the event of a RGT100-PEI overdose (defined as any dose above the applicable DL), the Investigator should report such an overdose via the SAE form immediately and closely monitor the subject for AEs. The Investigator will use clinical judgement to treat any overdose.

Treatment is to be discontinued prematurely in the following situations:

- Complete response
- All injectable lesions have disappeared
- Intolerance of study treatment
- Subject withdrawal

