9 TIMING OF STUDY PROCEDURES

Participants will undergo a screening period of up to 3 weeks. The study treatment period will be approximately 4 weeks (shorter if the subject withdraws, and longer if there are delays to dosing due to toxicities). All subjects will be followed up for 30 days following their final dose of RGT100-PEI or until resolution or stabilization of all treatment-related AEs, whichever is later. If no progressive disease (PD) is seen after a 30-day follow-up period, subjects will be in follow-up for another 30 days (total of 60 days after last injection), which defines the end of the trial. Further survival follow-up will be performed every 3 months for a period of 24 months outside of the main study.

Subjects will provide written informed consent before any study-related procedures are performed. The timing of study assessments is provided in Table 3 for Group A and Table 4 for Group B.

Table 3: Group A (Cutaneous) Schedule of Assessments

Trial Visits, Investigations, and Interventions	Screening	Treatment Period								End-of- Treatment Visit	Follow-up Visit		
	Day -21 to Day -1	Week 1		Week 2		Week 3		Week 4		Week 5	Week 9	Week 13 ^a	
		Day 1 Inj 1	Day 4 Inj 2	Day 8 Inj 3	Day 11 Inj 4	Day 15 Inj 5	Day 18 Inj 6	Day 22 Inj 7	Day 25 Inj 8	Day 29 (±3 days)	30 days after last injection (±7 days)	60 days after last injection (±7 days)	
RGT100-PEI injection ^a		+	+	+	+	+	+	+	+				
Informed Consent	+												
Medical History	+												
Eligibility Criteria	+												
Pregnancy Test ^b	+									+			
ECG	+									+	+	+	
Physical Examination ^c	+	+		+		+		+		+	+	+	
ECOG Performance Status	+	+		+		+		+		+	+	+	
Vital Signs ^d	+	10+	10+	5+	5+	5+	5+	5+	5+	+	+	+	
Overnight observation		+	As deemed appropriate by the investigator										
Height/Weight	+												
Hematology ^e	+	++	+	++	+	++		++		+	+	+	
Clinical Chemistry ^e	+	++	+	++	+	++		++		+	+	+	
Urinalysis ^e	+	++	+	++	+	++		++		+	+	+	
Autoimmunity ^f	+					+				+	+		
Infectious Diseases ^g	+									+	+		
Immunoglobulins ^h	+					+				+	+		
Immuno-monitoring ⁱ	+	+++							+++	+	+	+	
PK (RGT100-PEI) ^j		7+							7+				
Mutation Status ^k	+												
Tumor Assessment and Photography ^l	+	+		+		+		+		+	+	+	

Trial Visits, Investigations, and Interventions	Screening	Treatment Period								End-of- Treatment Visit	Follow-up Visit	
	Day -21 to Day -1	Week 1		Week 2		Week 3		Week 4		Week 5	Week 9	Week 13 ^a

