11.1.2 Datasets or Populations Analyzed

All subjects enrolled in the study will be accounted for. The number of subjects who were NE, who died, or who withdrew before treatment began will be recorded. All subjects who received at least 1 dose of the study drug will be included in the analysis for toxicity.

Two subject populations will be used for the analyses:

- The safety population will consist of all enrolled subjects who received at least 1 dose of RGT100-PEI.
- The evaluable population will consist of all enrolled subjects who complete Week 4 or withdraw early for experiencing a DLT.

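### The evaluable set for dose escalation omits the missed-injection rule in Section 8.3.4.2, and that rule does not say whether a late, made-up injection counts as missed

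*Combined protocol and SAP*

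**What the plan says.** **Who counts.** Section 11.1.2 defines the evaluable population as "all enrolled subjects who complete Week 4 or withdraw early for experiencing a DLT". Section 11.1.2.1 applies the same definition to dose escalation: "All evaluable subjects will be analyzed for dose escalation, which are those completing Week 4 or those withdrawing early for experiencing a DLT". Neither mentions a number of injections.

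**Who is replaced.** Section 8.3.4.2 replaces, for DLT evaluation, subjects who miss more than 2 injections (Group A) or more than 1 (Group B) because of drug-related toxicity that is not a DLT.

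**How dosing can slip.** Section 8.4.9.4 interrupts treatment for grade 3, grade 4 or intolerable grade 2 toxicity. It then says "Trial treatment will be permanently discontinued if the subject fails to recover to this extent within 3 weeks", and, on missed doses generally, "If a dose is missed, the dose should be administered as soon as possible". Section 9 allows the treatment period to be "longer if there are delays to dosing due to toxicities". Section 8.4.9.1 reads differently. For Group B it says "The total dose will be administered on 1 day of every week for a maximum of 4 weeks", and it sets the same four-week maximum for Group A.

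**The window.** Section 8.4.7 says "The DLT period will be 4 weeks", and the MTD definition in 8.4.8 uses the same length. Section 8.3.4.2 equates the DLT period with four weeks of treatment, and Section 10.5 has the Safety Review Committee (SRC) meet after subjects complete four weeks of treatment. Under 8.4.9.1 the dose escalation meeting "will be held to evaluate a dose escalation after all subjects in a DL per group have completed the DLT period".

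**The concern.** In a 3+3 design a subject without a DLT is informative only to the extent that the planned doses were given and observed. Section 8.3.4.2 recognises this by limiting missed injections, but the analysis definition drops the limit. Two things follow. The reported DLT table can include subjects whom the escalation decision excluded. In addition, because the rule speaks only of missed injections while 8.4.9.4 has missed doses made up, a site could keep a subject whose remaining injections were postponed past Day 28. A grade 3 event after one of those injections would not be a DLT if the window is 28 calendar days.

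The subjects at issue are those held for toxicity that is not a DLT under 8.4.7, mainly intolerable grade 2 events and exempt grade 3 tumor flare. An exempt grade 3 immune-related event must resolve within 7 days, so it gives only a short hold.

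**Working it through.** **1. Denominator.** Suppose three subjects meet 8.3.4.2 with no DLT, and a fourth was replaced under that section but stayed through Week 4. The decision rests on 0 of 3. By 11.1.2.1 the table shows 0 of 4. Likewise a decision on 1 of 6 (16.7%) is reported as 1 of 7 (14.3%). No arithmetic error is involved: two sections give two denominators.

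**2. Late injections.** Inputs: the planned days in Tables 3 and 4 (A: 1, 4, 8, 11, 15, 18, 22, 25; B: 1, 8, 15, 22) and the 3-week limit and 2-day minimum spacing in 8.4.9.4. Assumption: the hold runs from the skipped injection day to the day of resumption, at most 21 days. If the 3 weeks run from an earlier toxicity onset, dosing must resume sooner and the counts fall. Late means after Day 28.

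| Hold | Planned spacing resumed | Late | Catch-up every 2 days | Late |
|---|---|---|---|---|
| A, 7 days from Day 8 | 1, 4, 15, 18, 22, 25, 29, 32 | 2 | 1, 4, 15, 17, 19, 21, 23, 25 | 0 |
| A, 10 days from Day 15 | 1, 4, 8, 11, 25, 29, 32, 36 | 3 | 1, 4, 8, 11, 25, 27, 29, 31 | 2 |
| A, 21 days from Day 8 | 1, 4, 29, 32, 36, 39, 43, 46 | 6 | 1, 4, 29, 31, 33, 35, 37, 39 | 6 |
| A, 21 days from Day 22 | 1, 4, 8, 11, 15, 18, 43, 46 | 2 | 1, 4, 8, 11, 15, 18, 43, 45 | 2 |
| B, 7 days from Day 8 | 1, 15, 22, 29 | 1 | 1, 15, 17, 19 | 0 |
| B, 14 days from Day 8 | 1, 22, 29, 36 | 2 | 1, 22, 24, 26 | 0 |
| B, 21 days from Day 8 | 1, 29, 36, 43 | 3 | 1, 29, 31, 33 | 3 |
| B, 21 days from Day 22 | 1, 8, 15, 43 | 1 | 1, 8, 15, 43 | 1 |

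If the 2-day minimum means two clear days, catch-up runs every 3 days. The A 7-day case then has 1 late injection (15, 18, 21, 24, 27, 30). The other late counts do not change.

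**3. What 8.3.4.2 does with these.** If a late injection counts as missed, the most that can be outstanding in a retained subject is 2/8 = 1/4 = 25% of cycle 1. If it does not, there is no cap, and the maximum is 6 of 8 (A) or 3 of 4 (B). Catch-up does not reduce that maximum, because a 21-day hold from Day 8 resumes on Day 29.

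**4. What one such subject could do (illustration).** Assume equal DLT hazard per injection, a full-cycle DLT rate p, a fixed window, and one of the first three subjects with only 25% of injections inside it. That subject's DLT probability is p1 = 1 − (1 − p)^0.25. With q = 1 − p and q1 = 1 − p1:

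P(escalate) = q1·q² + (p1·q² + 2·q1·p·q)·q³

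- p = 0.33: p1 = 0.095, so 0.406 + 0.443 × 0.301 = 0.54. At full exposure, q³ + 3p·q⁵ = 0.43.
- p = 0.25: p1 = 0.069, so 0.523 + 0.388 × 0.422 = 0.69. At full exposure, 0.60.

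This is the extreme case. At the tolerated 75% exposure in one subject, the same formula with exponent 0.75 gives 0.47 and 0.63.

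**5. The window.** Under 8.4.7 and 8.4.8 the plain reading is 28 days. Under 8.3.4.2 and 10.5 the period can be read as lasting until four weeks of treatment have been given. On that reading late injections fall inside it and the SRC waits. No section chooses between the two.

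**The case against.** The strongest reply is that the plan already controls exposure. Section 8.3.4.2 governs who counts in the 3+3 decision, and it deliberately accepts 2 of 8 or 1 of 4 injections missed. That stands. A reader might infer from 11.1.2 that the plan has no exposure requirement for DLT evaluation. The documents do not support this: the requirement exists but is not carried into the analysis definition.

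A reader might also infer that the SRC will necessarily decide while cycle-1 injections are outstanding. That needs a window fixed in calendar days, and the wording of 8.3.4.2 and 10.5 leaves another reading open. The text supports an ambiguity and no more.

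Catch-up dosing also weakens the milder examples: it removes every late injection in the 14-day Group B case and brings the 10-day Group A case down to the tolerated 2. The large counts need a non-DLT toxicity lasting about three weeks from early in the cycle.

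Further mitigations are real. The investigator and the sponsor physician can call another related toxicity a DLT, although the lead-in to 8.4.7 limits DLTs to events within the period. The SRC also reviews new safety information from preceding cohorts. Section 11.1 defers detail to a separate SAP and 10.5 to an SRC charter. The supplied text includes neither, so the matter could be settled there. Even so, 8.4.9.4 uses the word missed for a dose that is given later, which suggests that made-up doses do count as missed without saying so.

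**Conclusion.** The point holds as a minor inconsistency. Following 11.1.2.1 as written gives a DLT denominator that can include subjects replaced under 8.3.4.2, so the reported table can differ from the decision. Section 8.3.4.2 leaves late, made-up injections undefined: read one way, exposure outside the window is capped at 25% of cycle 1; read the other way, it can reach 75% (6 of 8 or 3 of 4). The DLT period has two wordings.

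The 75% figure rests on a 28-day window, on late injections not counting as missed, and on a full 21-day hold from Day 8. The escalation probabilities also assume a DLT rate and an equal hazard per injection, neither of which the documents give. A reader might take those probabilities as evidence that escalation in this trial is materially biased. The documents do not support that: they give no rate of toxicity holds, and the number of subjects affected is unknown and probably small.

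**What to change.** - In 8.3.4.2, state that an injection not given by Day 28 because of toxicity counts as missed, even if it is given later.
- In 11.1.2 and 11.1.2.1, define a DLT-evaluable subject as one who has a DLT, or one who completes the 28-day DLT period with no more than 2 (A) or 1 (B) such missed injections.
- Use one definition of the DLT period in 8.3.4.2, 8.4.7, 8.4.8 and 10.5, and reconcile the four-week maximum in 8.4.9.1 with the delays allowed in 8.4.9.4 and 9.

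The cost is wording and an occasional extra replacement. A subject who catches up by Day 28, such as the 14-day Group B case, would be retained, which is reasonable because all injections were given within the window. Up to 2 (A) or 1 (B) late injections would still fall outside it, as 8.3.4.2 already tolerates. The SRC should review events after those injections as safety data.

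Extending the DLT period to the last cycle-1 injection for delayed subjects would close that remainder too. It could move the SRC decision to 46 − 28 = 18 days (A) or 43 − 28 = 15 days (B) past Day 28, so it is a trade-off for the sponsor and not a necessary correction.

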11.1.2.2 Dose Expansion

All subjects who received at least 1 dose of the study drug will be included in the analysis.

11.1.3 Demographic and Other Baseline Characteristics

11.1.3.1 Demographic data

Characteristics of the subjects, including medical history and disease characteristics at baseline, will be listed for each subject and summarized for the total sample and by DL and cohort. Medical history findings will be summarized using Medical Dictionary for Regulatory Activities (MedDRA) terms. Reasons for discontinuation of investigational product will be listed including the study day of treatment discontinuation and will be summarized by DL and group.

11.1.3.2 Exposure

Exposure to investigational product (i.e., total amount of study drug received) will be listed for all subjects by group and DL.

Total exposure (date of last dose minus date of first dose+1) and total time on study (date of discontinuation minus date of first dose+1) will be summarized by the following: mean, standard deviation, minimum, maximum, median, and number of observations. In addition, the number and percentage of subjects with at least 1 dose interruption/dose delay will be presented separately for each DL and group.

Relative dose intensity and percentage intended dose for RGT100-PEI will be derived and summarized by the following: median, minimum, maximum, 75th percentile, 25th percentile and number of observations. Relative dose intensity is the percentage of actual dose intensity delivered relative to the intended dose intensity through treatment discontinuation. Percentage intended dose is the percentage of the actual dose delivered relative to the intended dose through progression.

11.1.4 Efficacy Variables

11.1.4.1 Tumor response

Tumor response will be assessed to support the secondary objectives of the study. Tumor response data will be listed and summarized by cohort and visit (that includes disease assessment) using the following response categories: CR, PR, SD, PD, NE, early death from malignant disease, early death from toxicity, early death from other cause, or unknown (not assessable, insufficient data). The results of lesion measurements, changes in size and supportive laboratory parameters will be analyzed and summarized. Evaluations at screening and at Day 1 will serve as baseline values. Changes from baseline for continuous variables and shift tables for categorical variables will be presented by cohort and by visit of tumor assessment. Descriptive statistical methods as outlined in detail in the SAP will be used.

Objective response rate as defined by achieving CR or PR will be presented by percentage rates and 95% confidence intervals assuming an exact binomial distribution (Clopper–Pearson method). Fisher’s exact test (univariate analyses) and logistic regression may be used to compare the response rates of the different cohorts.

The duration of response (DR) will only be calculated for subjects who have an objective response. The DR is calculated from the date of the first documented response until the date of progression or death; subjects who continue to respond at the date of data cut-off (last subject last visit) will be censored at their last known date. Summaries of DR (n, medians, quartiles) will be provided.

11.1.4.2 Tumor Mutation Assessments

Tumor response data will be summarized by mutation status. Logistic regression analyses may be used to test potential predictive factors (BRAF if available from the site, human papilloma virus, mismatch repair status, PD-1/PD-L1 expression) for overall response.

11.1.4.3 Pharmacokinetics

Standard PK parameters will be calculated by use of validated PK software. The definitions of the PK parameters and the equations used to calculate them will be provided in the SAP. A listing of PK sampling dates and times will be provided. Plasma concentrations of RGT100-PEI will be summarized by nominal sample time. Plasma concentrations and derived PK parameters for RGT100-PEI will be summarized by cohort using descriptive statistics (n, geometric mean, arithmetic mean, standard deviation and coefficient of variation, minimum, maximum). Values below the limit of quantification will be set to zero but excluded from the calculation of the geometric mean.

No adjustments for pre-planned multiple comparisons will be made.

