6.3.3 Nonclinical Pharmacokinetic Studies of RGT100-PEI

Initial *in vitro* stability assays of uncomplexed and complexed RGT100 duplex showed that uncomplexed RGT100 exhibited an elimination half-life of 2 to 4 hours (plasma/serum). Complexed RGT100, however, was stable for over 48 hours *in vitro* in plasma and serum. Therefore, it was concluded that, once decomplexed, RGT100 is rapidly degraded within the human body.

In vivo availability studies and initial toxicokinetic studies in CD-1 mice have revealed that RGT100-PEI can be detected in the plasma for up to 30 minutes after systemic administration. Major target organs for distribution are liver, spleen, and lung, where it can be detected for over 24 hours. Longer time spans have not yet been assessed.

Toxicokinetic data from 14-day dose range-finding studies, as well as 28-day toxicity studies, in CD-1 mice and cynomolgus monkeys have demonstrated that exposure to RGT100-PEI by intravenous (IV) and subcutaneous (SC) administration is dose-related but nonlinear, slight accumulation is seen over time, and elimination after IV administration is fairly rapid.

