6.4 Dose Selection and Justification

Based on the pharmacodynamic data and the dose/tumor size correlation observed (refer to IB, Section 4.2.1.4), 0.2 mg RGT100 can be considered a pharmacologically active dose for intratumoral injection when extrapolated from tumors in mice to a human lesion with a diameter of 20 mm.

Accordingly, a starting dose (DL1) of 1 mL (0.2 mg) of RGT100-PEI is being considered for the first-in-human clinical study of intratumoral/intralesional injection into cutaneous or hepatic lesions. Results from the 4-week toxicity studies in mice and cynomolgus monkeys suggest the following NOAELs and human equivalent doses (HEDs) after IV administration of RGT100-PEI:

- NOAEL/maximum tolerated dose (MTD) in mice = 1.6 mg/kg IV → HED = 0.13 mg/kg
- NOAEL in cynomolgus monkeys = 0.16 mg/kg → HED = 0.05 mg/kg
- MTD in cynomolgus monkeys = 1.5 mg/kg → HED = 0.5 mg/kg

Leakage of RGT100-PEI from the lesion after intratumoral injection is expected to be marginal because, after intratumoral injection in mice, 100% of the compound remained local

(refer to IB, Section 4.2.1.4). However, for the calculation of safety margins, complete leakage (eg, accidental administration into a blood vessel) was used as a worst case assumption. A theoretical complete leakage from a cutaneous lesion was mimicked in the SC toxicity studies. Local toxicity after direct injection into the liver was not examined, but results from a preliminary biodistribution study showed that most RGT100 is found in the liver after IV injection. Therefore, the IV toxicity data can be used to extrapolate the safety of leakage into healthy liver tissue.

Thus, assuming a theoretical complete systemic ad hoc exposure after intratumoral administration, a starting dose of 1 mL (0.2 mg RGT100) in a 60 kg human (0.0033 mg/kg) would lead to the following safety factors (calculated with unrounded raw data):

- Safety factor for mouse NOAEL/MTD: $0.13/0.0033 = 40$
- Safety factor for cynomolgus monkey NOAEL: $0.05/0.0033 = 15$
- Safety factor for cynomolgus monkey MTD: $0.5/0.0033 = 150$

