A standard 3 + 3 design ([Table 1](#)) will be used for dose escalation (3 subjects per DL group, with the potential to add an additional 3 subjects to a DL group if toxicity is observed).

Table 1: Standard 3+3 Dose Escalation Scheme

Number of Subjects with a DLT at a Given Dose Level (during the DLT period)	Action
0 out of 3 subjects experience a DLT	Escalate to the next DL
1 out of 3 subjects experiences a DLT	Enter 3 additional evaluable subjects at the current DL for a total of 6 evaluable subjects
1 out of 6 subjects experiences a DLT	Escalate to the next DL

2 or more subjects (up to 6 subjects) experience a DLT	Dose escalation will be stopped (at this DL the MTD has been exceeded or declared)
--	--

Abbreviations: DL = dose level; DLT = dose-limiting toxicity; MTD = maximum tolerated dose.

If more than 2 subjects experience a DLT at a particular DL, a lower (or intermediate) DL may be explored to better define the MTD. Refer to [Section 8.4.6](#) for DLT definition and [Section 8.4.7](#) for MTD definition.

Approximately 9 to 24 subjects will be treated in each group during the dose escalation. All types of tumors that are accessible for intratumoral/intralesional injection may be treated in the dose escalation part of the study.

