10.2 Pharmacokinetic Variables

Analysis of plasma samples for the determination of RGT100-PEI will be carried out to assess systemic exposure to locally injected RGT100-PEI. Blood samples for the determination of RGT100-PEI levels will be collected before (maximum 30 minutes) injection and 5 and 30 minutes, 2, 4, 6, and 24 hours post injection on Week 1 Day 1 and on Week 4 Day 25 (Group A) or Week 4 Day 22 (Group B). Windows for sample collection are: 5 minutes (± 2 minutes), 30 minutes (± 5 minutes), 2 hours (± 10 minutes), 4 hours (± 30 minutes), 6 hours (± 30 minutes), and 24 hours (± 2 hours).

Handling and processing details will be outlined in the Laboratory Manual for the RGT100-001 protocol.

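### The below-quantification rule for plasma concentrations puts the two means on different subjects, so the geometric mean is biased upward and can exceed the arithmetic mean

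*Combined protocol and SAP*

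**What the plan says.** Section 11.1.4.3 fixes the rule itself and does not leave it to the later SAP: "Values below the limit of quantification will be set to zero but excluded from the calculation of the geometric mean". The same section says "Plasma concentrations of RGT100-PEI will be summarized by nominal sample time" and asks, by cohort, for "descriptive statistics (n, geometric mean, arithmetic mean, standard deviation and coefficient of variation, minimum, maximum". That list has a single n. It has no median, no BLQ count and no separate n for the geometric mean, and nothing says what to show when most or all values at a time point are BLQ. The synopsis PK paragraph lists similar statistics and has no BLQ rule.

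Three other places bear on how often the rule will operate:

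- Section 8.1.1 sets the cohort size: "3 subjects per DL group, with the potential to add an additional 3 subjects to a DL group".
- Section 10.2 sets the sampling times: a pre-dose sample, then "5 and 30 minutes, 2, 4, 6, and 24 hours post injection on Week 1 Day 1", repeated in Week 4.
- On expected exposure, section 6.4 says "Leakage of RGT100-PEI from the lesion after intratumoral injection is expected to be marginal", and section 6.3.3 reports for CD-1 mice that "RGT100-PEI can be detected in the plasma for up to 30 minutes after systemic administration".

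**The concern.** A geometric mean cannot use zeros, so some exclusion or substitution is unavoidable. The difficulty is that the two means are printed side by side under one n while resting on different sets of subjects, and that the subjects dropped from the geometric mean are always those with the lowest concentrations. In a cohort of 3 to 6, one BLQ value removes 1/6 = 17% to 1/3 = 33% of the data behind the geometric mean.

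Section 10.2 gives the purpose of PK sampling as assessing systemic exposure after local injection. In a first-in-human trial that is the human check on the assumption of little leakage. If one subject in six has measurable drug, the geometric mean describes that subject alone. The bias also grows with the BLQ share. Since that share should fall as dose rises, the comparison between dose levels is distorted as well as each level.

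**Working it through.** **Inputs.** From the protocol: the BLQ rule (11.1.4.3), 3 or 6 subjects per dose level (8.1.1), and six post-dose samples of which four are at 2 hours or later (10.2). Not in the protocol: the LLOQ, the between-subject CV and the BLQ share. These are assumptions, shown as ranges. The plan states no PK figure, so there is none to reproduce.

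**Step 1: the rule as formulas.** With n subjects and k quantifiable values x, AM = (sum of x)/n and GM = exp[(sum of ln x)/k].

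**Step 2: small cohorts (arbitrary units).**

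| Values | AM | GM |
|---|---|---|
| 10, BLQ, BLQ | 10/3 = 3.33 | 10 |
| 2, 5, BLQ | 7/3 = 2.33 | √10 = 3.16 |
| 2, 3, 5, 8, BLQ, BLQ | 18/6 = 3.00 | 240^(1/4) = 3.94 |
| 10 and five BLQ | 10/6 = 1.67 | 10 |
| 1.5, 20, BLQ | 21.5/3 = 7.17 | √30 = 5.48 |
| 2, 3, 5, 8, 12, BLQ | 30/6 = 5.00 | 2880^(1/5) = 4.92 |
| all BLQ | 0 | undefined |

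For one set of positive values the GM cannot exceed the AM. Under this rule it can, though the fifth and sixth rows show that it need not.

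**Step 3: when the order reverses.** If the quantifiable values are log-normal, their own AM/GM ratio is √(1+CV²). Zeros for a BLQ share f multiply the AM by (1−f). So GM > AM when f > 1 − 1/√(1+CV²): 4% at CV 30%, 11% at 50%, 18% at 70%, 29% at 100% and 45% at 150%.

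**Step 4: size of the bias.** Let true concentrations be log-normal with median 1 and σ = √ln(1+CV²), and place the LLOQ at the f-quantile, with normal quantile z. In a large cohort, reported GM / true median = exp[σφ(z)/(1−f)]. At CV 100% (σ = 0.833) and f = 50% this is exp(0.833 × 0.399/0.5) = 1.94. For cohorts of six with at least one quantifiable value, simulation (400,000 cohorts per setting) gives a mean ratio of:

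| CV | 20% BLQ | 50% BLQ | 80% BLQ |
|---|---|---|---|
| 30% | 1.1 | 1.3 | 1.5 |
| 50% | 1.2 | 1.5 | 2.0 |
| 100% | 1.4 | 2.05 | 3.4 |
| 150% | 1.6 | 2.6 | 5.1 |

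The largest cell can be checked directly. Given k quantifiable values, the expected GM is m^k, with m = exp[σ²/(2k²)] × Φ(σ/k − z)/(1−f). With σ = 1.086 and z = 0.842 this is 5.38, 4.91 and 4.79 for k = 1, 2, 3 (probabilities 0.393, 0.246, 0.082) and about 4.7 for larger k (0.017). The weighted sum is 3.79, and 3.79/0.738 = 5.14.

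Cohorts with no quantifiable value have no GM: 0.5⁶ = 1.6% of cohorts at 50% BLQ and 0.8⁶ = 26% at 80% BLQ.

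**Step 5: comparison across dose levels.** Assume CV 100%, one LLOQ, 80% BLQ at DL1 and 20% BLQ at DL4. The true medians then differ by exp[0.833 × (0.842 + 0.842)] = 4.06, close to the dose ratio 0.8/0.2 = 4. The large-cohort factors are 3.21 at DL1 and 1.34 at DL4, so the reported ratio is 4.06 × 1.34/3.21 = 1.7. A roughly fourfold rise would be reported as less than twofold.

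**Step 6: substitution by LLOQ/2.** In the same simulation, counting all cohorts, the GM with LLOQ/2 substituted averages about 0.8 to 1.7 times the true median for 50% to 80% BLQ and CV 30% to 150%. That is closer than the plan's rule but not neutral.

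**The case against.** **How often BLQ values occur.** A reader might infer that the protocol expects most samples from 2 to 24 hours to be BLQ. It does not say so. The 30-minute figure is from mice after systemic dosing. Section 6.3.3 also reports that complexed RGT100 was stable in plasma and serum for more than 48 hours in vitro, and slight accumulation over time in mice and monkeys. Taken literally, the statement in 6.4 that "after intratumoral injection in mice, 100% of the compound remained local" points to time points with every value BLQ, where the geometric mean is undefined and not inflated. This stands: BLQ values are likely, but their share is unknown.

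**What the tables would still show.** The arithmetic mean, minimum and maximum are reported too, and a minimum of 0 would reveal that some value was BLQ. Section 11.1.5 lists a median for continuous variables in general, and section 12.5 promises data listings. This softens the point. It does not tell a reader how many values lie behind the geometric mean, and the PK-specific list leaves the median out.

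**Consequence.** PK is an exploratory objective and endpoint (7.1, 7.2). A reader might infer that dose selection is exposed. The documents do not support that: section 11.1.6 bases the recommended dose on DLTs, and where no MTD is reached section 8.4.8 names safety, tolerability, clinical benefit and pharmacodynamic data. Overstating exposure at one dose is also the cautious direction for safety. That holds for the level but not for the slope, since step 5 shows that a rise with dose can be understated.

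**The later SAP.** A more detailed SAP is promised and may add a BLQ count. The rule itself is already set in the protocol, and no other BLQ rule appears in the documents.

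**Conclusion.** The point holds as a reporting defect of limited reach. At any nominal time with both BLQ and quantifiable values, the two means rest on different subjects. The geometric mean is biased upward, and it can exceed the arithmetic mean. The different subject sets and the possible reversal follow from the stated rule and need no distributional assumption.

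The size does need assumptions. For log-normal concentrations, cohorts of six and at least one quantifiable value, the ratio to the true median is about 1.3 to 2.6 at 50% BLQ and 1.5 to 5.1 at 80% BLQ, over CV 30% to 150%. At 20% BLQ it is 1.1 to 1.6.

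It would be too strong to say that the geometric mean always exceeds the arithmetic mean, as the counter-examples in step 2 show. The arithmetic mean is not the safe alternative either, because setting BLQ values to zero biases it downward. What is affected is the exploratory description of systemic exposure and its comparison across dose levels; no sample size, test, escalation step or recommended-dose rule depends on it. It is worth correcting because the correction is almost free.

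**What to change.** In section 11.1.4.3, and in the SAP that implements it:

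- At every nominal time, report n, the number and percentage of BLQ values, and the n behind each mean.
- Add the median to the PK statistics.
- Do not report a geometric mean when more than half of the values are BLQ; show the median and range instead. The one-half cut-off is a convention, so state it in advance. It also covers time points where every value is BLQ.
- If a single substitution such as LLOQ/2 is wanted for both means, present it only as a sensitivity summary, since it is not neutral (step 6).

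The cost is a sentence or two of text, one or two extra table rows, and no geometric mean at some late time points. Sampling, assays and trial conduct do not change.
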